Objective(s):	The primary objective of this study is to evaluate safety following use of ECHELON ENDOPATH Staple Line Reinforcement (ECHELON SLR) in subjects undergoing indicated gastric and lung resection procedures. The secondary objective will be to capture usability data of the device.				
Overview of Study Design:	This prospective, single-arm, multi-center study will collect clinical data in a post-market setting by procedure group (gastric and lung resection). Investigators will perform each procedure using the device in compliance with their standard surgical approach and the ECHELON SLR instructions for use (IFU).				
	Subjects will be consented and screened anytime during a period of 8 weeks prior to the date of surgery. Subjects will be considered treated when at least one ECHELON SLR has been placed during the procedure. All treated subjects will be followed post-operatively through discharge and again at 28, 70, and 135 days (± 14 days) post-surgery; therefore, from the surgery date to study exit, the duration will be approximately 19 weeks.				

Number of Subjects:

A minimum of 243 treated subjects (maximum of 431 treated subjects) will be included in the study from up to 16 sites in the United States with the following procedure targets:

- A minimum of 112 treated subjects for gastric procedures; and
- A minimum of 131 treated subjects for lung resection procedures.

Given the lack of available clinical data on the ECHELON SLR, an adaptive approach to sample size re-estimation will occur after approximately 50% of the originally planned sample size in each group has been enrolled. The purpose of this interim analysis will be to estimate the rate of the primary endpoint in each procedure group as well as to understand the size of the relative reduction in the rate of the primary endpoint in relation to published literature. Based on these observed values, the sample size will be re-estimated. Upon completion of the sample size re-estimation, the Sponsor will determine if enrollment will continue to the originally planned enrollment values above (the minimum number listed above for each procedure group), stop at the time of the interim analysis due to futility, or increase the sample size in one or both groups if the true endpoint rate or effect size differ from the original estimates.

Criteria for Inclusion:

Subjects satisfying the following criteria will be considered eligible for enrollment in this study:

- 1. Primary procedure (gastric or lung resection) where the ECHELON SLR is planned to be used for reinforcement of staple lines per the IFU in either a or b:
 - a. Gastric procedures limited to laparoscopic gastric resection, robotic laparoscopic gastric resection, partial gastrectomy, gastric wedge resection, subtotal gastrectomy, laparoscopic Roux-en-Y gastric bypass, and robotic laparoscopic gastric bypass; or
 - b. Lung resection procedures that include lobectomy, segmentectomy or wedge resection, and lung volume reduction surgery, and may be video assisted thoracic surgery (VATS) or open procedures;
- Willingness to give consent and comply with all study-related evaluations and visit schedule; and
- 3. At least 18 years of age.

Criteria for Exclusion:

Subjects meeting any of the following criteria will be considered ineligible for enrollment in this study:

Preoperative

- Physical or psychological condition which would impair study participation;
- 2. Gastric procedures: Body mass index (BMI) ≥ 50.0 kg/m², or lung resection procedures: BMI ≥ 46.0 kg/m²;

	 The procedure is a revision/reoperation for the same indication or same anatomical location; 					
	4. A	proce	dure where extended wound or	organ support is required;		
	Any medical condition that the investigator deems could impact inflammatory or immune response;					
			ent treatment with medications to could have influence on wound h			
	Po	olydiox	ory of hypersensitivity to polyglactin (Vicryl®), rdioxanone (PDO or PDS), or hypersensitivity to related ducts (cross-allergy); or			
		Enrollment in a concurrent interventional clinical study that could impact the study endpoints.				
	Intraoperative					
	 Per surgeon discretion, presence of adhesions that could lead to an increased risk of leak occurrence at a different location than the staple line. Per surgeon discretion, medical finding intraoperatively such that the procedural plan is changed and ECHELON SLR is not used during the procedure. 					
Test Product(s):	ECHELON SLR:					
restrioduct(s).			I	D : 6		
	Product Code		Description	Reinforcement Length		
	ECH60F	?	ECHELON ENDOPATH™ Staple Line Reinforcement	60mm		
Reference Therapy/Product:	No comparator product is being used in this study.					
Duration of Treatment:	Subjects will be exposed to the study device during the procedure and will be followed for approximately 135 days. The device will be used as indicated in the IFU. The ECHELON SLR is composed of materials that are essentially absorbed within 120 days.					
Criteria for Evaluation:	Primary endpoint: • Incidence of device-related adverse events (AEs) through the 70-day post-procedure follow-up visit. Specific device-related AEs that will be captured and counted toward the primary endpoint are listed below. • Gastric • Bleeding (defined as below)					
	Occurrence of post-operative blood transfusion deemed related to bleeding at the staple line; or					

Trial Number: ESC_2018_03 Version: Amendment 3 – Gastric procedures only

- Return to operating room before 70-day post-procedure follow-up visit due to bleeding deemed related to the staple line;
- Leak (defined as below)
 - Occurrence of intra-operative or postoperative gastrointestinal leak related to the staple line as documented intra-operatively, by clinical exam, or radiographically;
- Stricture (defined as below)
 - Occurrence of stricture documented radiographically or by endoscopy along the staple line;
- o Lung Resection
 - Prolonged air leak deemed related to the staple line (defined as below)
 - Greater than postoperative day 7 (procedure=day 0);
 - Empyema (defined as below)
 - Purulent fluid collection in the pleural space documented radiographically, excluding chronic empyema

Secondary performance endpoints:

- Number of study devices replaced during surgery due to slipping or bunching or not properly loaded onto stapler cartridge; and
- Device questionnaire by procedure group (gastric and lung resection) to capture usability.

Statistical Analysis:

Analysis Sets

The summary of all performance and safety endpoints will be performed on the set of subjects in whom the ECHELON SLR is utilized during the surgical procedure. The summary of all primary and secondary endpoints will be performed by procedure group (gastric or lung resection).

Primary Endpoint Analyses

The following hypotheses will be evaluated for the primary endpoint for gastric procedures:

 $H_0: p_G \ge 14.0\%$ $H_1: p_G < 14.0\%$

Where p_G is the percentage of subjects experiencing at least one occurrence of bleeding, leak, or stricture through 70 days. A 95% confidence interval will be calculated for p based on the sample proportion of subjects experiencing the endpoint using the Normal approximation to the Binomial distribution, and the upper limit of this confidence interval will be compared to 14.0% to evaluate the above hypotheses. A p-value will be determined based on the same Normal

Trial Number: ESC_2018_03 Version: Amendment 3 – Gastric procedures only

approximation methodology.

A similar methodology will be applied to the data observed in lung procedures to evaluate the following hypotheses:

 $H_0: p_L \ge 12.0\%$

 H_1 : $p_L < 12.0\%$

Where p_L is the percentage of subjects experiencing at least one occurrence of prolonged air leak or empyema through 70 days.

Secondary Endpoint and Safety Analyses

Summary statistics will be provided by procedure group for all procedurerelated variables measured in this study including number of study device(s) replaced during surgery due to slipping or bunching and device questionnaires to capture usability. Counts and percentages will be provided for number of staple line reinforcement devices used during the procedure.

All device- and procedure-related AEs reported during the study will be coded to the Medical Dictionary for Regulatory Activities (MedDRA). Adverse events will be assessed for seriousness, severity, action taken, and outcome. Adverse events will be summarized by MedDRA system organ class and preferred term by procedure group and in total. Serious AEs will be summarized in a similar manner.

TABLE OF CONTENTS

	Page
PROTOCOL SIGNATURE PAGE	2
INVESTIGATOR SIGNATURE PAGE	
CLINICAL TRIAL PROTOCOL SYNOPSIS	
PROTOCOL-SPECIFIC ACRONYMS AND ABBREVIATIONS	11
ETHICS	12
ADMINISTRATIVE REQUIREMENTS	

6.4.3 Reporting Serious Adverse Events	
7.0 PRODUCT COMPLAINTS	
7.1 REPORTING PRODUCT COMPLAINTS FOR MARKETED DEVICES	
7.1.1 Reporting of Approved EES Marketed Devices	
8.0 REFERENCES	33

PROTOCOL-SPECIFIC ACRONYMS AND ABBREVIATIONS

Acronyms/Abbreviations Terms

ADE Adverse device effect

AE Adverse event

ASA American Society of Anesthesiologists

BMI Body mass index

CFR Code of Federal Regulations

C-SATS Crowd-sourced assessment of technical skills

ECHELON SLR ECHELON ENDOPATH™ Staple Line Reinforcement

eCRF Electronic case report form
EDC Electronic Data Capture
EES Ethicon Endo-Surgery, Inc.
FDA Food and Drug Administration

GCP Good clinical practice

ICD Informed consent document

IFU Instructions for use

IRB Institutional review board

MedDRA Medical Dictionary for Regulatory Activities

PI Principal Investigator

SADE Serious adverse device effect

SAE Serious adverse event SAP Statistical analysis plan

SOC Standard of care

USADE Unanticipated serious adverse device effect

VATS Video-assisted thoracic surgery

ETHICS

Institutional Review Board

Participating investigators will ensure that this protocol, Informed Consent Document (ICD), ICD or protocol amendments, and if applicable, any other written information provided to the subjects that assist in the decision to participate are reviewed by an Institutional Review Board (IRB) that complies with governmental requirements. The approving IRB will be responsible for the initial and continuing review and approval of this clinical study. Participating investigators will be required to promptly report to the IRB as required by the IRB's policies. Additionally, investigators will be required to refrain from making any changes in the clinical investigation plan without Sponsor and IRB approval of an amended protocol, except where necessary to eliminate apparent immediate hazards to study subjects or others.

Applicable Regulations

This study will be conducted in compliance with GCP and in accordance with the Declaration of Helsinki, as well as any other applicable local and country regulatory requirements.

Subject Information and Consent

Regulations concerning the protection of subjects require that informed consent be obtained before a subject may participate in any clinical study. An IRB approved informed consent must be sought from each subject and must be appropriately documented in the subject's medical record prior to initiating the study. It is the Investigator's responsibility to obtain written informed consent from the subject, the Investigator may delegate this responsibility if appropriately documented.

The informed consent process involves the following: giving a subject adequate information concerning the study, providing adequate time for the subject to consider all available options, responding to the subject's questions, ensuring that the subject has comprehended this information and finally, obtaining the subject's written consent to participate in this study. All subjects in this study should be completely informed about the purpose, risks, benefits, and other pertinent details of this study. The informed consent process is careful to avoid the perception of any coercion or undue influence on, or inducement of, the subject to participate, and does not waive or appear to waive the subject's legal rights. The ICD is presented in native, non-technical language that is understandable to the subject.

Prior to a subject's participation in this study, an ICD will be signed and dated by the subject and person who conducted the consent discussion. The subject will be provided a copy of the signed ICD. The ICD and any other written materials provided to the subject to assist in the decision to participate must be revised whenever new information becomes available that may be relevant to their willingness to participate or continue participation in this study. Revision to the ICD and other written materials will receive IRB approval before implementation. Each subject will be required to sign any amended ICD (as required by the IRB) and will receive a copy of the signed ICD.

ADMINISTRATIVE REQUIREMENTS

This study is sponsored by Ethicon Endo-Surgery, Inc. (EES, Cincinnati, OH, USA) and will be conducted in up to sixteen surgery centers in the United States under a single protocol approved by each participating site's IRB prior to implementation. The principal investigator at each study site is a surgeon qualified by education, experience, and training to perform the study procedure and to assume responsibility for the conduct of this study.

The Data Management and Biostatistics groups of the Sponsor will be responsible for the analysis of data from this protocol. An Electronic Data Capture (EDC) system will be utilized by study site personnel to transfer study data from source records (the first point of clinical data capture) onto common electronic case report forms (eCRFs). This system is a web-based, secure electronic software application (Medidata® Rave, [name]). This system was designed and is developed and maintained by Medidata in a manner that is compliant with national and international GCP data protection/data privacy and electronic record/electronic signature (e.g. 21 Code of Federal Regulations [CFR] Part 11) regulatory requirements.

Protocol Modifications

All protocol amendments must be issued by the Sponsor, signed and dated by the Investigator, and should not be implemented without prior IRB approval, except where necessary to eliminate immediate hazards to the subjects or when the change(s) involves only logistical or administrative aspects of the study (e.g., change in medical monitor(s), change of telephone number(s)). The Investigator reports the protocol amendments to the IRB as per their local requirements.

1.0 INTRODUCTION

Staple line complications are an important issue to consider in gastric and lung resection surgical procedures. Various types of staple line reinforcement devices currently exist and are used for reinforcing staple lines including fibrin glue and other sealants, suture oversewing, and buttressing. For buttressing, some of the most commonly used reinforcement buttressing materials include bovine pericardium and biocompatible glycolide copolymer.

The Sponsor, EES, has developed the ECHELON ENDOPATH Staple Line Reinforcement (ECHELON SLR) for use in surgical procedures in which soft tissue transection or resection with staple line reinforcement is needed. ECHELON ENDOPATH Staple Line Reinforcement can be used for reinforcement of staple lines during lung resection and bariatric surgical procedures. The device can also be used for reinforcement of staple lines during gastric, small bowel and colorectal procedures.

2.0 STUDY OBJECTIVES

The primary objective of this post-market study is to evaluate safety following use of the ECHELON SLR in subjects undergoing indicated gastric and lung resection procedures. The secondary objective will be to capture usability data of the device.

2.1 PRIMARY ENDPOINT

The primary endpoint for this study is the incidence of device-related AEs through the 70-day post-procedure follow-up visit. Specific device-related AEs that will be captured and counted toward the primary endpoint are listed below.

- Gastric
 - Bleeding (defined as below)
 - Occurrence of post-operative blood transfusion deemed related to bleeding at the staple line; or
 - Return to operating room before 70-day post-procedure follow-up visit due to bleeding deemed related to the staple line;
 - Leak (defined as below)
 - Occurrence of intra-operative or post-operative gastrointestinal leak related to the staple line as documented intra-operatively, by clinical exam, or radiographically;
 - Stricture (defined as below)
 - Occurrence of stricture documented radiographically or by endoscopy along the staple line;
- Lung Resection
 - Prolonged air leak deemed related to the staple line (defined as below)
 - Greater than postoperative day 7 (procedure=day 0);
 - Empyema (defined as below)
 - Purulent fluid collection in the pleural space documented radiographically, excluding chronic empyema

2.2 SECONDARY PERFORMANCE ENDPOINTS

The secondary performance endpoints for this study are listed below.

 Number of study devices replaced during surgery due to slipping or bunching or not properly loaded onto stapler cartridge; and

• Device questionnaire by procedure group (gastric and lung resection) to capture usability.

2.3 ADDITIONAL KEY DATA COLLECTED

Additional key data collected for evaluation in this study are:

- Endocutter and reload used (type, name, and color [for reload]) for each firing during the procedure along with which firings are associated with the study device;
- Total number of study devices used during the procedure;
- If intervention used for intra-operative bleeding on the staple line, capture type and number of interventions used:
- Occurrence of blood transfusion (record the total required units of blood, rationale, and if related to staple line);
- Date(s) of chest tube placement and removal, daily volume and characteristics of chest tube drainage;
- · Air leak duration in lung resection procedures;
- Surgical procedure conducted (and technique used);
- Procedure duration;
- Hospital stay duration; and
- Readmission for procedural-related complications.

3.0 INVESTIGATIONAL PLAN

3.1 OVERALL STUDY DESIGN AND PLAN - DESCRIPTION

This prospective, single-arm, multi-center study will collect clinical data in a post-market setting by procedure group (gastric and lung resection). Investigators will perform each procedure using the device in compliance with their standard surgical approach and the ECHELON SLR IFU.

Subjects will be consented and screened anytime during a period of 8 weeks prior to the date of surgery. Subjects will be considered treated when at least one ECHELON SLR has been placed during the procedure. All treated subjects will be followed post-operatively through discharge and again at 28, 70, and 135 days (± 14 days) post-surgery; therefore, from the surgery date to study exit, the duration will be approximately 19 weeks.

3.2 STUDY POPULATION

3.2.1 Enrollment

Subjects will be recruited from the PI's existing patient population who plan to have an elective gastric or lung resection surgical procedure. Eligible subjects will be consecutively approached for participation so as to remove the potential of subject selection bias. Subjects will be considered enrolled at the time of consent signing. Subjects will be considered treated when at least one ECHELON SLR has been placed during the procedure. Gastric procedures are limited to laparoscopic gastric resection, robotic laparoscopic gastric resection, partial gastrectomy, gastric wedge resection, subtotal gastrectomy, laparoscopic Roux-en-Y gastric bypass, and robotic laparoscopic gastric bypass. Lung resection procedures include lobectomy, segmentectomy or wedge

resection and lung volume reduction surgery, and may be VATS or open procedures. Up to 16 centers in the United States will be selected as study sites. Each participating investigator is expected to perform a minimum of five gastric or lung resection procedures using the ECHELON SLR. A minimum of 243 treated subjects (maximum of 431 treated subjects) are planned to be in the study with a minimum of 112 treated subjects for gastric procedures and a minimum of 131 treated subjects for lung resection procedures.

3.2.2 Inclusion Criteria

Subjects satisfying the following criteria will be considered eligible for enrollment in this study:

- 1. Primary procedure (gastric or lung resection) where ECHELON SLR is planned to be used for reinforcement of staple lines per the IFU in either a. or b.:
 - a. Gastric procedures limited to laparoscopic gastric resection, robotic laparoscopic gastric resection, partial gastrectomy, gastric wedge resection, subtotal gastrectomy, laparoscopic Roux-en-Y gastric bypass, and robotic laparoscopic gastric bypass; or
 - b. Lung resection procedures that include lobectomy, segmentectomy or wedge resection, and lung volume reduction surgery, and may be VATS or open procedures;
- 2. Willingness to give consent and comply with all study-related evaluations and visit schedule; and
- 3. At least 18 years of age.

3.2.3 Exclusion Criteria

Subjects meeting any of the following criteria will be considered not eligible for enrollment in this study:

Preoperative

- 1. Physical or psychological condition which would impair study participation;
- 2. Gastric procedures: Body mass index (BMI) ≥ 50.0 kg/m², or lung resection procedures: BMI ≥ 46.0 kg/m²;
- 3. The procedure is a revision/reoperation for the same indication or same anatomical location;
- 4. A procedure where extended wound or organ support is required;
- 5. Any medical condition that the investigator deems could impact inflammatory or immune response;
- 6. Concurrent treatment with medications that the investigator deems could have influence on wound healing;
- 7. History of hypersensitivity to polyglactin (Vicryl®), Polydioxanone (PDO or PDS), or hypersensitivity to related products (cross-allergy); or
- 8. Enrollment in a concurrent interventional clinical study that could impact the study endpoints.

Intraoperative

- 1. Per surgeon discretion, presence of adhesions that could lead to an increased risk of leak occurrence at a different location than the staple line.
- 2. Per surgeon discretion, medical finding intraoperatively such that the procedural plan is changed and ECHELON SLR is not used during the procedure.

3.2.4 Screening Failures

All subjects signing consent who do not have at least one ECHELON SLR placed during their procedures will be recorded as screen failures. For subjects who are determined to be screen failures, only the relevant eCRF pages (inclusion/exclusion criteria, demographics, AEs, subject completion/discontinuation) will be completed.

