5.6 ANALYSIS SETS

The summary of all performance and safety endpoints will be performed on the set of subjects in whom the ECHELON SLR is utilized during the surgical procedure. The summary of all primary and secondary endpoints will be performed by procedure group and in total.

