5.9.4 Primary and Secondary Endpoint Analyses

Within each procedure group, the number and percentage of subjects experiencing an occurrence of the primary endpoint will be summarized and a 95% confidence interval for each rate will be estimated. The performance goal hypotheses will be tested based on methodology as described above in Section 5.4.

The number and percentage of subjects experiencing each component of the composite endpoint will be summarized in each procedure group.

All device-related and procedure-related AEs reported during the study will be coded to MedDRA. All AEs will be summarized by MedDRA system organ class and preferred term by procedure group and in total. Separate summaries will be provided for device-related and procedure-related AEs. Serious AEs will be summarized in a similar manner.

Counts and percentages will be provided for usability data collected via surgeon questionnaire and summary statistics will be provided for the number of study devices attempted and used during the surgical procedure.

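### A case in which every attempt to use the reinforcement fails becomes a screen failure and leaves the device-replacement endpoint, so that result can err only in the device's favour

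*Protocol*

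**What the plan says.** Usability is the study's second aim: "The secondary objective will be to capture usability data of the device" (Protocol 2.0). Protocol 2.2 and SAP 8.4.2 measure it by two endpoints: "Number of study devices replaced during surgery due to slipping or bunching or not properly loaded onto stapler cartridge; and" the investigator questionnaire.

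Who counts is settled in three places.

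- Protocol 3.1: "Subjects will be considered treated when at least one ECHELON SLR has been placed during the procedure".
- Protocol 3.2.4, for everyone else who consented: "All subjects signing consent who do not have at least one ECHELON SLR placed during their procedures will be recorded as screen failures". For them, "only the relevant eCRF pages (inclusion/exclusion criteria, demographics, AEs, subject completion/discontinuation) will be completed".
- Protocol 5.6, repeated in SAP 6: performance and safety endpoints are summarised in "the set of subjects in whom the ECHELON SLR is utilized during the surgical procedure".

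The replacement count, the number of devices used and the firing-by-firing record are surgical variables (Protocol 3.4.2). Protocol 5.9.4 adds that "summary statistics will be provided for the number of study devices attempted and used during the surgical procedure". Replacements are also product complaints (Protocol 3.4.2), and complaints about any device in the procedure must be documented (Protocol 7.1.1).

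**The concern.** A usability result should include the cases in which the device could not be used. Here, a subject is counted as treated only after at least one device was placed, which is itself part of the outcome being measured.

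Take a procedure in which the first device bunches, the second will not load, and the surgeon staples without reinforcement. This is the most complete handling failure possible, yet the rules as worded appear to remove it from the handling endpoint. A reader who sees a low replacement count in the study report could not tell whether complete failures were absent or left out. An adverse event caused by the failed attempt would meet the adverse-device-effect definition in Protocol 6.1.2, which covers malfunction, but might not reach the device-related tables.

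**Working it through.** The plan states no replacement or abandonment rate, so there is no figure to reproduce. The check is to trace two kinds of case through the documents and then illustrate the size.

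**Step 1. Trace the cases.**

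| Record | At least one device placed | Every attempt failed, none placed |
|---|---|---|
| Status (Protocol 3.1, 3.2.4) | Treated | Screen failure |
| Device-use, replacement and firing data (Protocol 3.4.2) | Collected | Not among the four page types |
| Analysis set (Protocol 5.6, SAP 6) | In | Out, unless *utilized* includes failed attempts |
| AE summaries (SAP Tables 12–16, Analysis Set) | In | Out, on the same reading |
| AE page and Listing 26 (All Subjects) | In | In |
| Product complaint (Protocol 7.1.1) | Documented | Documented |

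**Step 2. Look for anything that puts the failed case back.**

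- Intraoperative exclusion 2 (Protocol 3.2.3) explains non-use by a medical finding. No section deals with non-use caused by device failure; 3.2.4 treats both alike.
- The SAP has no complaint table or listing.
- Video might show the failure, but Protocol 4.3 lets only site-reported data count for endpoints.
- The All Subjects listings of intraoperative and firing data (13 and 14) can show only what was collected.
- SAP Table 1 lets a reader subtract the analysis set from those consented, but not see why subjects were untreated. The completion page is kept and goes to Listing 32, but device failure is not a named reason in Protocol 3.2.5 or Table 1 and would fall under *other*.

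Nothing restores the case to the replacement endpoint.

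**Step 3. Check the terms.** Neither *placed* nor *utilized* is defined. If *utilized* includes failed attempts, 5.6 admits subjects for whom 3.2.4 collects no surgical data. If it does not, they are excluded. The replacement data are missing either way. Protocol 5.2 adds to the confusion by saying that all enrolled subjects will have the device utilized, while 3.2.4 provides for enrolled subjects without one.

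**Step 4. Check the endpoint wording in treated subjects.** The count is of devices *replaced*. Read literally, a device that slipped and was removed with nothing put in its place is not counted.

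**Step 5. Illustrate direction and size.** Let N be treated subjects, R those with at least one replacement, and F the cases in which every attempt failed. N is the planned minimum (Protocol 3.2.1); R and F are assumptions.

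- Rate without the failed cases: R/N
- Rate with them: (R+F)/(N+F)
- Difference: F(N−R) / [N(N+F)], which is positive whenever F > 0 and R < N

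| Group | R/N | F=1 | F=3 | F=5 | F=10 |
|---|---|---|---|---|---|
| Gastric | 6/112 = 5.4% | 7/113 = 6.2% | 9/115 = 7.8% | 11/117 = 9.4% | 16/122 = 13.1% |
| Gastric | 2/112 = 1.8% | 3/113 = 2.7% | 5/115 = 4.3% | 7/117 = 6.0% | 12/122 = 9.8% |
| Lung | 7/131 = 5.3% | 8/132 = 6.1% | 10/134 = 7.5% | 12/136 = 8.8% | 17/141 = 12.1% |

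With F = 0 nothing changes. The plan's endpoint is a count of devices, not a per-subject proportion, so the table shows sensitivity and does not predict a planned result. For a total count of failed devices the direction is the same, since the omitted cases can only add to it.

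**The case against.** The best defence is that this is a narrow gap in a descriptive endpoint. A treated-subject set is a common choice in a single-arm device study, the endpoint carries no hypothesis, and Protocol 3.4.2 foresees several devices per procedure. One successful placement keeps the subject, with every replacement in that procedure, in the data. Nothing in the documents suggests how often all attempts fail. All of this stands, and it limits the weight of the point.

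It also rules out four stronger readings that a reader might infer.

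- *The whole usability objective loses these failures.* The questionnaire is answered by investigators about their own experience after their 1st, 3rd and 5th procedures (Protocol 3.4.3). That section does not say whether an abandoned case counts as one of those procedures, and nothing stops such a case from colouring a later answer.
- *The summary of devices attempted and used cannot be produced.* It can be for treated subjects, whose used and replaced devices are both recorded. Only the case with no placement is missing.
- *The failures vanish.* They remain as product complaints, and any adverse event is in Listing 26.
- *The plan will report a per-subject failure rate that is wrong by a known amount.* The plan defines no such rate, and its table shells contain no table for the replacement endpoint at all.

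One might also answer that a device fired and then found bunched could count as utilized. That is possible, but it does not recover pages that 3.2.4 does not call for.

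**Conclusion.** The point holds in a limited form. For a subject in whom every attempt failed and no device was placed, Protocol 3.2.4 removes the surgical, firing and replacement data. Protocol 5.6 and SAP 6, on the reading that *utilized* excludes failed attempts, then remove the subject from the replacement endpoint and from Tables 12–16. Separately, the word *replaced* leaves out devices removed without replacement in treated subjects.

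Any resulting bias in the handling-failure result favours the device. Its size cannot be determined from the documents: it is zero if no such case occurs, and the illustrated movements rest entirely on assumed counts. The primary hypotheses are unaffected. This is worth correcting because it is a stated rule that selects the usability population on the usability outcome, but it does not threaten the study's main conclusion.

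**What to change.** 1. Define *placed* (Protocol 3.1, 3.2.4) and *utilized* (Protocol 5.6, SAP 6), and reconcile them with each other and with Protocol 5.2.
2. In Protocol 3.2.4 and 5.6 and SAP 6, add a *device attempted* set: consented subjects in whom a device was loaded, or loading was tried, for the study procedure.
3. For these subjects, require the existing device-use and endocutter-firing pages and the reason why no device was placed.
4. Report the replacement endpoint in that set, worded as devices replaced or removed without replacement for slipping, bunching or failed loading, and give it a table shell. Report adverse events arising from the attempt in the same set.
5. Keep the treated set for the primary endpoint.

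If the forms can no longer change, tabulate consented but untreated subjects by reason, reconciled with the complaint records.

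The cost is wording in both documents, one or two extra pages for what should be a few subjects, and possibly a slightly less favourable usability figure.
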